The rationale for the duration of the interventions, follow up, and blinding procedures: The proposed study is of standard duration for the geriatric population requiring 12 weeks or longer trials to document antidepressant efficacy.

4.0 *Research Design and Methods: Describe in detail the design and methodology of the study.

Subjects: We anticipate screening about 100 subjects to recruit 60 older depressed adults (>60 y.o.) who will be randomized to receive 20-120 mg of levomilnacipran blindly with increment dose titration 20 mg per day -3 days; 40 mg per day-3 days. Based on efficacy and tolerability, we will increase by 40 mg per day each following week 2nd-4th week the maximum recommended doses is 120 mg per day. The comparison group will receive similar blinded titration with matching placebo. Doses of the drugs will be adjusted according to individual tolerability and safety. We expect an attrition rate of about 10% based on our prior experience thus 54 subjects will complete the study. Patients will be assessed pre-treatment; and then weekly during the first four weeks and bi-weekly thereafter. At all visits, clinical ratings of mood, vital signs, and safety will be obtained. Inclusion criteria: 1) The presence of a major depressive disorder diagnosed according to the DSM-IV criteria. 2) A 24-item Hamilton Rating Scale for Depression (HAMD) score of 17 or higher at baseline. 3) Mini-Mental State Exam (MMSE) score > 24.

Exclusion criteria: subjects will be excluded if they had 1) any current and/or lifetime history of other psychiatric disorders (except unipolar depression with or without comorbid generalized anxiety disorder), or 2) recent unstable medical or neurological disorders; 3) any disabilities preventing their participation in the study or in the MRI; 4) diagnosis of dementia; 5) acute suicidality; 6) those with known allergic reactions to milnacipran, uncontrolled narrow angle glaucoma, seizures, poorly-controlled hypertension or ischemic changes on ECG, serotonin syndrome, or the recently used MAOIs within last 4 weeks; 7) ineligible for MRI (e.g., metal in the body or claustrophobia)

Primary outcome will be measured and defined as follows: 1) Remission will be defined as HAMD scores of 6 or less for three consecutive weeks and at week 12; 2) Improvement in depression severity using HAMD scores.

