Randomization and treatment schedule: After all screening and baseline test results are reviewed and eligibility criteria are confirmed, medications will be dispensed if patients continue to meet eligibility criteria and sign the informed consent form. All eligible subjects will be randomized to levomilnacipran or placebo group using a computer-generated random assignment scheme, which assigned subjects in a 1:1 ratio to each group. Randomization will be done prior to subject s being assigned to the groups.

Follow up assessment: The follow up will take place weekly for the first four weeks of treatment, every two weeks for the remainder of the study. Each follow up assessment will include measures of efficacy and safety. The weekly frequency of contact with all subjects will serve as an additional safeguard to monitor worsening of depression, as well as the emergence of side-effects or suicidal ideations.

Study medications and treatment procedures. Subjects will be randomized to: 1) LMIL20-120 mg per day or 2) matching placebo. The allowed range of the drugs according to tolerability and efficacy assessments will be between 20-120 mg per day for LMILN. The dose finding procedures will be only performed in the first four weeks and after that will remain stable until the end of the acute trial, as it worked in our pilot study. We will assess the optimal dose of LMIL based on tolerability and safety in this population. The balance will be maintained between the efficacy and tolerability of medications. If symptoms worsen, the study drug will be tapered and discontinued. Subjects will be referred for clinical care at UCLA or the community. The PI will continue the observation for safety until the appointment is scheduled with the primary psychiatrist. The dose will be titrated according to the titration schedule, including if side-effects are mild or well tolerated and if CGI scores for improvement is 3 or higher. The titration rate is based on the currently recommended titration to achieve the greatest efficacy that may not work for geriatric patients. For that reason, we have safeguards against rapid titration with potential side-effects that will require a slower titration or staying at a lower dose.

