The MRI scanning procedure requires that you be confined in a small partially enclosed space. Some individuals find this to be uncomfortable and may exhibit symptoms of claustrophobia including nervousness, sweating or other minor discomfort. The sound of the MRI scanner can be quite loud; the subject will be given special ear plugs to minimize the noise. In addition, the magnetism of the machine attracts certain metals; therefore, people with these metals within their bodies (such as pacemakers, infusion pumps, aneurysm clips, metal prostheses, joints, rods, or plates) will be excluded from the study. The metal in dental fillings is less responsive to magnetism and is therefore allowed. The MRI technician will ask you if you have any metals within your body. The subjects will be expected to notify the investigator conducting the study of any metal implants, other than dental fillings. There are no other known side effects resulting from exposure to the MRI scan.

Depression monitoring.

The weekly frequency of contact with all subjects will serve as an additional safeguard to monitor worsening of depression, as well as the emergence of side-effects or suicidal ideations.

- 1. If a patient demonstrates worsening of their symptoms or no response by week 8 or during follow up (i.e., CGI-I score > 3) of treatment, they will be discontinued from the study and referred for appropriate clinical services.
- 2. Suicidal ideations with the HAMD item 3 score of 3 or greater
- 3.The participants will take 20-120 mg of LMIL per day with titration in blinded 40 mg pills prepared by the UCLA pharmacy. The only concomitant psychotropic medication allowed in the trial is lorazepam, 1 of mg or less a day. If patients are not able to tolerate these medications, they will be discontinued from the trial.

The PI will withdraw subjects and discontinue the study treatment if the subject demonstrates worsening symptoms. The study drug will be tapered and discontinued and subjects will be referred for clinical care at UCLA or the community. The PI will continue the observation for safety until the appointment is scheduled with the primary psychiatrist.

Risk/Benefit Analysis

4.0 *RISKS/BENEFIT ANALYSIS: Indicate how the risks to the participants are reasonable in relation to anticipated benefits, if any, to participants and the importance of the knowledge that may reasonably be expected to result from the study:

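### In weeks 1–4 a participant who has worsened but tolerates the drug meets both the titration condition and the discontinuation rule, with no stated priority; for unchanged participants the timing is ambiguous

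*Combined protocol and SAP*

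**What the plan says.** The titration rule is in section 10.1, item 4.0 (Research Design and Methods).

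- The Subjects paragraph gives a starting sequence by days, then says "we will increase by 40 mg per day each following week 2nd-4th week", depending on efficacy and tolerability, up to 120 mg per day. Placebo receives a similar blinded titration.
- Study medications and treatment procedures limits the window: "The dose finding procedures will be only performed in the first four weeks and after that will remain stable". It applies the schedule when side effects are tolerable and "if CGI scores for improvement is 3 or higher".

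The exit rules are in four places.

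- Study medications and treatment procedures, a few sentences before the titration condition: "If symptoms worsen, the study drug will be tapered and discontinued". No week and no threshold are attached.
- Section 14.1, Depression monitoring: participants who show worsening, or "no response by week 8 or during follow up (i.e., CGI-I score > 3) of treatment, they will be discontinued from the study".
- Section 15.2, item 3.1 (interim safety analysis) and item 5.1 (withdrawal rules) carry the same CGI-I rule. Sections 14.1 and 15.2, item 5.1, also state withdrawal for worsening without a time limit.

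On timing, the Follow up assessment paragraph of section 10.1, item 4.0, says "The follow up will take place weekly for the first four weeks of treatment" and every two weeks after that. Measures and Outcomes has CGI rated at all visits.

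**The concern.** A single CGI-I score can satisfy an instruction to continue titrating and an instruction to stop the drug. Two raters or two clinicians following the same application could act differently on the same participant, and both would be compliant.

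Three things are at stake. First, the dose reached: the lay summary in section 2.2 names dose finding as a purpose, and titration is confined to the weeks in which the conflict arises. Second, withdrawal: it depends on the outcome being measured, so an unclear rule makes the pattern of missing data depend on local interpretation. Third, the week-12 imaging and cognitive measures. Both are scheduled at baseline and 12 weeks only. The symptom, comorbidity and quality-of-life scales add an assessment on early termination; the imaging and neuropsychological schedules do not.

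**Working it through.** **1. The plan's own retention figure.** Section 10.1, item 4.0, expects about 10% attrition among 60: 60 × (1 − 0.10) = 54. This reproduces and is not contested. It is attributed to prior experience, with no stated allowance for withdrawal under the CGI-I rule.

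**2. Thresholds.** The gloss in the exit rule attaches scores above 3 to worsening or lack of response, so higher is worse.

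| CGI-I score | Titration condition (3 or higher, side effects tolerable) | Exit rule (above 3) |
|---|---|---|
| Below 3 | not met | not met |
| Exactly 3 | met | not met |
| Above 3 | met | met, if the exit rule is in force at that visit |

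The thresholds overlap only above 3. The application does not say where, above 3, lack of response ends and worsening begins.

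**3. Time windows.**

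| Rule | Window stated |
|---|---|
| Titration | first four weeks; increases in weeks 2–4 |
| Taper and stop for worsening | none, so any week |
| Discontinue for no response | by week 8, or during follow up |

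**4. Crossing the two.**

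- *Worsened participants.* The worsening rule has no start week, so it is in force in weeks 1–4 on any reading. A worsened participant scores above 3 and so also satisfies 3 or higher. If side effects are tolerable, both instructions apply, and no section ranks them.
- *Unchanged participants, reading A.* Non-response is judged from week 8 onward. Titration ended at week 4, so the rules run in sequence and do not conflict.
- *Unchanged participants, reading B.* The words *during follow up* include the weekly visits of weeks 1–4. Both rules then apply at those visits.

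Readings A and B part company most for someone above 3 early who would have reached 3 or below by week 8: retained under A, withdrawn under B. Someone still above 3 at week 8 is withdrawn under either; only the timing and the dose reached differ.

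**5. Limits on the overlap.** The titration condition needs tolerable side effects, so poor tolerability removes it. It also needs room to increase: from 40 mg in 40 mg steps to 120 mg there are (120 − 40) / 40 = 2 steps, so a participant at the maximum has no increase left.

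**6. Size.** No section gives a CGI-I distribution, so the number meeting both rules cannot be computed. As arithmetic on an assumption only: if a share q of the 54 expected completers were withdrawn under the CGI-I rule, completers would be 54 × (1 − q).

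| Assumed q | Completers |
|---|---|
| 10% | 48.6, about 49 |
| 20% | 43.2, about 43 |
| 40% | 32.4, about 32 |
| 60% | 21.6, about 22 |

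This shows how the retention figure responds to the discontinuation rule as a whole. The ambiguity governs only part of any such loss, because week-8 withdrawals occur on either reading.

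**The case against.** The strongest reply has four parts.

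*The follow-up paragraph is a visit schedule, not a definition.* This stands. Elsewhere in section 10.1 the term means a later assessment compared with baseline (dementia screening) or the 12-week scan (Hypothesis 3, item 6.0). If it meant every visit from week 1, naming week 8 would add little. Reading A is therefore plausible. A reader might infer that unchanged participants certainly face both rules in weeks 1–4; the documents allow that reading but do not settle it.

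*Withdrawal for worsening can be taken as overriding.* It is stated flatly and repeated, while titration is conditional. A sensible clinician may well read it so. But no sentence says so, worsening has no threshold, and the titration condition sets no upper bound on the score. The conflict between the written rules remains.

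*Not every score above 3 triggers both rules.* This stands, because of the tolerability condition and the dose ceiling.

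*The primary analysis is not shown to lose anyone.* This also stands. HAM-D is collected on early termination, Hypothesis 1 uses a mixed model over time, and dropouts are classified by reason. A reader might infer that withdrawn participants leave the analysed population; no section says that. Nor do the documents show different rules by arm.

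**Conclusion.** The point holds in a limited form. For participants who have worsened in weeks 1–4 and tolerate the drug, the application gives two opposite instructions on any reading. For unchanged participants the conflict exists only if *during follow up* reaches back to the weekly visits. For scores of 3 or below these rules do not conflict.

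A reader might go further and conclude that who remains in the trial is undefined, or that a large fraction of the 60 is affected. The documents do not support either. Retention is ambiguous only for scores above 3 in the early weeks, and any count would need an assumed share of early non-response together with the contested reading.

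The consequence that can be stated is qualitative. The dose reached and the timing of outcome-dependent withdrawal depend on which section is followed, and week-12 imaging and cognitive data are exposed because no early-termination assessment is stated for them. It should be corrected because it is a contradiction between written rules that bears on safety and on who stays on treatment.

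**What to change.** Reconcile section 10.1, item 4.0 (Study medications and treatment procedures) with section 14.1 (Depression monitoring) and section 15.2, items 3.1 and 5.1, so that:

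- each CGI-I score in each visit window leads to one action, identical in both arms;
- where two conditions can be met together, the order of priority is written down;
- *worsening*, *no response* and *during follow up* are each given a meaning for these rules, and all sections use the same text.

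Which action applies, and how the discontinuation window relates to the titration window, is for the investigators to decide. No view is taken here on which clinical rule is right. The cost is a wording amendment, with no added visits or measurements.

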Imaging Biomarkers: Imaging data will be acquired from each subject at baseline and at 12-weeks post-randomization on a Siemens 3T Trio system using a 32-channel head coil. Each scanning session will last 60 minutes and include 1) a T1-weighted multi-echo MPRAGE (MEMPR) sequence with real time motion correction53 for the examination of brain structure and for use in network analyses; 2) a matched bandwidth T2 sequence for the detection and quantification of WMHs and CSF; 3) rs-fMRI to examine treatment related changes in functional activity at rest and intrinsic network connectivity; and 4) high angular resolution diffusion imaging (HARDI) to isolate changes in white matter microstructure and structural connectivity. Both rs-fMRI and diffusion imaging will utilize recently developed accelerated multiband pulse sequences with optimized spatial and temporal resolution (Table 3).54,55 Notably, the same multimodal imaging protocol has been implemented for a NIH study addressing biomarkers of geriatric depression in association with escitalopram both with and without augmentation of memantine treatment. In a separate extramurally funded project, we are also using this protocol to examine treatment effects and brain aging associated with Kundalini yoga. We are thus able to pool data and/or contrast results across studies as might be appropriate.

Resting State fMRI: During acquisition of blood-oxygen-level-dependent (BOLD) rs-fMRI data, subjects will remain awake with their eyes closed. Preprocessing will occur in a parallelized supercomputing environment using FSL56-58 and custom processing modules. Independent components analysis (ICA),59,60 will estimate the optimal number of components for each subject and time point and identify components representing artifacts. After low pass filtering (0.1-0.01 Hz) and transformation into atlas space, the best-fit default mode network (DMN) and executive and memory function network will be selected for each subject/time point for higher-level analysis. In follow-up analyses, seed regions-of-interest (ROIs) will be employed to examine voxel-level correlations between particular network nodes.60-62 In addition to subtracting changes between baseline and follow-

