up scans to determine associations with clinical response and neuropsychological function, we will represent fMRI maps as statistical change maps in time, with each voxel representing a smooth change in magnitude (positive or negative) from the baseline dataset. Notably, resting state activations are highly reproducible over time63 and experience-based neural plasticity in resting state connectivity has been shown over periods as short as 2-9 days.64 Recent research also shows significant changes in fronto-limbic connectivity in association with antidepressant treatment such as ECT65,66 as we have also shown [Fig. 3].

Diffusion Imaging: Diffusion data will be analyzed using FSL tools and include correction for slice prescription and residual eddy current distortions, tensor fitting, and tract based spatial statistics (TBSS)67 Changes in white matter FA, indicating fiber coherence and integrity, and radial, axial and mean diffusivity that point to changes in axonal structure and myelination, will then be examined across time and in relation to clinical outcome and neuropsychological function. Tractography methods will augment whole brain tract analysis and will be used to extract particular fronto-limbic fiber pathways using seed regions from both anatomical and functional imaging data. More sophisticated HARDI reconstruction techniques will be explored to determine more sensitive approaches for identifying changes in structural connectivity across treatment groups. Our previous data has shown increased FA and complementary decreases in mean and radial diffusivity in association with ECT and links with treatment-related clinical response that appear associated with processes of myelination (Lyden et al., 2014) [Fig. 4].

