Hypothesis 1: The primary analyses will focus upon HAM-D24 scores and will be analyzed using general linear mixed model analysis (e.g., SAS PROC MIXED). The two treatment groups will be compared for time course of HAM-D-24 with the initial endpoint EOT at 12 weeks. Covariates may be included in the model as noted above. In addition, likelihood ratio ?2 comparison will examine group differences in remission (HAM-D24 =6) and response (HAM-D24 =10) at EOT. Analyses for the cognitive outcome variables will be akin to those described above for the continuous HAM-D scores. As noted in the Neuropsychological Assessment section, there are four cognitive domains that are being assessed. Of these, the two primary cognitive domains of interest for this proposal are Cognitive Control and Episodic Memory. A separate general linear mixed model as above will be estimated using these two domain scores as dependent variables. The remaining domains, namely Verbal Fluency and Information Processing/Attention will be examined as secondary outcome measures. Apathy will be examined using the AES total score and quality of life using SF-36 scores in similar mixed models.

Hypothesis 2: We will examine adverse events in the two treatment groups. A detailed comparison of the number as well as type of side-effects in the two treatment groups will be conducted using chi-square tests.

Hypothesis 3: LMIL will lead to improved functional connectivity in brain network activity as measured with resting state (rs-) fMRI, and plasticity in brain macro- and micro-structure as measured with structural MRI and DTI compared to the PBO. To address these hypothesis, summary MRI measures (e.g., substructure volume, diffusion metrics) will be included in the GLMMs as "covariates of interest." For whole brain or structure voxel-level or point based measures (e.g., thickness or activation), the GLMMs will be implemented in R (www. R.org). Time (of scan) will be treated as a continuous variable with random intercepts and slopes to account for within-subject correlations between repeated measurements to assess change and interactions amongst the interventions. Difference scores between baseline and 12-week follow-up may be substituted for some analyses. FDR and/or permutation methods will be used to control for multiple anatomic comparisons in whole-brain contexts.

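### Resting-state networks are taken from a separate ICA of each scan, so a different decomposition at baseline and week 12 can look like a change in connectivity

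*Combined protocol and SAP*

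**What the plan says.** Section 10.1, item 4.0 (Imaging Biomarkers) plans two scans per patient: "Imaging data will be acquired from each subject at baseline and at 12-weeks post-randomization". Under Resting State fMRI, ICA "will estimate the optimal number of components for each subject and time point and identify components representing artifacts". After filtering and transformation to atlas space, "the best-fit default mode network (DMN) and executive and memory function network will be selected for each subject/time point for higher-level analysis". The plan gives no dimensionality and no rule for judging fit.

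The selected maps are then compared over time. Item 4.0 describes subtracting baseline from follow-up to look for associations with clinical response and cognition, and builds change maps "with each voxel representing a smooth change in magnitude (positive or negative) from the baseline dataset". Item 6.0 (Hypothesis 3) models scan time with random intercepts and slopes, and adds: "Difference scores between baseline and 12-week follow-up may be substituted for some analyses". The hypothesis served is that "LMIL will lead to improved functional connectivity in brain network activity as measured with resting state (rs-) fMRI", alongside structural MRI and DTI measures. Item 2.0 labels Aim 3 exploratory.

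One planned analysis does not depend on the number of components: "In follow-up analyses, seed regions-of-interest (ROIs) will be employed to examine voxel-level correlations between particular network nodes".

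**The concern.** A spatial ICA component is defined only relative to the decomposition that produced it. With more components, a network may divide into parts. With fewer, neighbouring networks may merge. If one scan of a patient is decomposed at one order and the other scan at another, the two best-fit maps may not represent the same network. Their voxelwise difference then mixes real change with a change in what is being measured.

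At stake is the functional-connectivity part of Hypothesis 3. It is exploratory, but the plan gives the study of neural mechanisms as its reason for a placebo rather than an active comparator. It also foresees pooling or contrasting these images with two other studies, which needs networks defined in one consistent way.

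**Working it through.** The plan gives no component count, no expected variation in order and no imaging power, so there is no figure of its own to reproduce. The check has three parts.

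**1. The text.** Order is set per scan, networks are selected per scan, and the selected networks go forward to analyses of change. So ICA is not used for denoising alone. Sections 10.1 items 4.0 and 6.0 describe no group decomposition, common dimensionality, template with a stated fit rule, dual regression, or sensitivity analysis on order. Atlas transformation aligns anatomy but does not make two components the same network. The FDR and permutation methods in item 6.0 deal with multiplicity only.

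**2. What randomisation protects.** Write the observed change in patient *i* as D_i = C_i + A_i, where C_i is true change and A_i is the part due to differing decompositions.

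- Expected arm difference in D = expected arm difference in C + [E(A | drug) − E(A | placebo)]. The bracket is zero unless treatment affects the decomposition at week 12.
- If A is independent of C, Var(D) = Var(C) + Var(A). The artefact then costs precision.
- Mean change within one arm = E(C) + E(A). Nothing forces E(A) to be zero, and randomisation does not help here. The same applies to correlating D with clinical response.

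**3. Simulated size, with no true change.** All settings are assumptions.

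*Ten sources* (two halves of a default mode network with time-course correlation 0.8, plus eight other networks; 3000 voxels, 180 volumes, 40 repeats). Going from 9 to 10 components lowered the best-fit match to the template from 0.95 to 0.68 and network strength from 3.22 to 2.29: (3.22 − 2.29)/3.22 = 28.9%. A re-run with 20 repeats gave 3.09 to 2.20, or 28.8%. That step crosses the true number of sources, with sparse networks and low noise. Beyond it almost nothing happened: strength at 10, 12, 15 and 20 components was 2.195, 2.195, 2.195 and 2.194. The 9-to-10 drop was only about 3% at higher noise, and at most about 2% with larger networks (250 voxels per node).

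*Fifteen two-node networks* (3000 voxels, 200 volumes, noise SD 2, 25 runs per cell). The outcome is the change in the z-score of the weaker node in the best-fit map. SE = SD/√25.

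| Components, scan 1 / scan 2 | Node correlation 0.6: mean (SD; SE) | Node correlation 0.8: mean (SD; SE) |
|---|---|---|
| 15 / 15 | −0.05 (0.96; 0.19) | +0.11 (0.93; 0.19) |
| 30 / 30 | +0.01 (0.13; 0.03) | −0.11 (1.09; 0.22) |
| 15 / 20 | −0.55 (0.91; 0.18) | −0.39 (1.10; 0.22) |
| 15 / 30 | −2.02 (0.55; 0.11) | −0.29 (0.75; 0.15) |
| 20 / 30 | −1.50 (0.83; 0.17) | −0.65 (0.86; 0.17) |

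Equal orders show no systematic shift. Unequal orders shift the measure clearly at correlation 0.6. At 0.8, two of the three shifts are within two SEs of zero. Equal order still leaves a run-to-run SD of 0.13 to 1.09. Part of that is scan noise, but it suggests that fixing the number of components alone is not enough. The maps need a shared spatial basis.

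**The case against.** The other side has four good points.

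- **The large effect is a threshold case.** It needs the order to cross the true number of sources in a favourable layout. Elsewhere a change in order did almost nothing. This stands, and it is why no single magnitude can be given.
- **Splitting is not written into the plan.** The text does not say that one component is kept per network or how best fit is judged. The attached proposal and the cited ICA references are not in the reviewed text and might say more. This stands too: the artefact is possible, not certain. But an unspecified selection rule gives no assurance of comparability.
- **Drug-related bias is not shown.** A reader might infer that levomilnacipran, by raising heart rate, shifts the estimated order and so biases the arm contrast. The documents do not support that. Section 10.1 item 3.0 and Section 14.1 item 3.0 list tachycardia or increased heart rate only as adverse events. Section 14.1 item 4.0 reports no pulse elevation in pilot subjects given milnacipran. Nothing links heart rate to component number.
- **The scope is limited.** Hypothesis 3 also rests on structural MRI and DTI. Hypothesis 4 concerns baseline predictors, so a between-scan artefact does not apply to it. The seed-ROI correlations are independent of model order, but the plan makes them follow-up analyses, so they are only a partial safeguard.

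What survives is that the lead resting-state analysis compares maps from two unrelated decompositions.

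**Conclusion.** The concern holds as a possibility of unknown size. As written, a difference in order or decomposition between a patient's scans can look like a change in connectivity. For the drug–placebo contrast, the main consequence is added noise in the exploratory resting-state part of Hypothesis 3. Bias would require treatment to affect the estimated order. Within-arm change maps and correlations with clinical response lack the protection of randomisation. The primary HAM-D analysis is untouched.

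Simulated effects run from negligible to about 29%, entirely according to assumed source layout, noise and component counts.

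It is tempting to turn this into a power loss. Suppose a share q of scans split independently and each split moves the measure by 1 SD of change. A 0.7 SD effect then becomes 0.7/√(1 + 2q(1 − q)). At q = 0.2 this is 0.7/√1.32 = 0.61, and at q = 0.3 it is 0.7/√1.42 = 0.59. Two-sided t-test power with 30 per arm would fall from 76% to 64% and 61%. The arithmetic is right, but q and the 1 SD shift are both invented inputs. The 0.7 SD is the generic two-sample figure in item 6.0, not an imaging effect. No power loss should be quoted.

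This is a cheap improvement to an exploratory analysis, not a threat to the trial's main result.

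**What to change.** In Section 10.1 item 4.0 (Resting State fMRI), with a matching line under Hypothesis 3 in item 6.0:

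1. Keep ICA of each individual scan for artefact identification and removal only.
2. Define the networks once, blind to arm, by group ICA at one fixed, prespecified dimensionality over all patients and both time points, or from a fixed template.
3. Derive every subject and time-point map from that common basis by dual regression in FSL.
4. Name the default mode, executive and memory components before unblinding.

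It would also help to report the per-scan estimated order by arm and visit, and to repeat the analysis at one other dimensionality. The first would show whether order differs between arms, and the second how far the result depends on the choice.

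The cost is one pipeline change in software the plan already uses, with no new scans, visits or patient burden. The downside is that individual differences in network layout are fitted slightly less closely.
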